1. LIST OF ABBREVIATIONS

Abbreviation	Definition	
AE	adverse event	
AGI	Analysis Group, Inc.	
CIOMS	Council for International Organizations of Medical Sciences	
CI	confidence interval	
EMA	European Medicines Agency	
ENCePP	European Network of Centres for Pharmacoepidemiology and	
	Pharmacovigilance	
FDA	Food and Drug Administration	
GEP	Good Epidemiological Practice	
GPP	Guidelines for Good Pharmacoepidemiology Practices	
Hb	hemoglobin	
HR	hazard ratio	
IRB	Institutional Review Board	
IEA	International Epidemiological Association	
IEC	Independent Ethics Committee	
IMDC	International Metastatic Renal Cell Carcinoma Database Consortium	
ISPE	International Society for Pharmacoepidemiology	
ISPOR	International Society for Pharmacoeconomics and Outcomes Research	
KPS	Karnofsky Performance Status	
LDH	lactate dehydrogenase	
LLN	Lower limit of normal	
LSLV	last subject last visit	
NCCN	National Comprehensive Cancer Network	
OS	overall survival	
PFS	progression free survival	
RCC	Renal cell carcinoma	
SD	standard deviation	
TTD	time to treatment discontinuation	

4. MILESTONES

Milestone	Planned date	
Start of data collection	July 2018	
End of data collection	September 2018	
For studies with primary data collection, enter the planned		
date for last subject last visit (LSLV). For studies with		
secondary data collection, enter the planned date on which		
the analytical dataset will be first completely available; the		
analytic dataset is the minimum set of data required to		
perform the statistical analysis for the primary objective(s).		
Final study report	January 2019	
Enter the planned date for approval of final study report.		
For NI PASS protocols, the final study report must be		
submitted within 12 months of the end of data collection.		

5. RATIONALE AND BACKGROUND

Renal cell carcinoma (RCC) is the most common kidney cancer, accounting for about 90% of all kidney cancers. ¹⁻³ It accounts for 2-3% of all adult malignancies with an estimated 63,000 incident cases and 14,000 deaths per annum in the United States. ⁴ Approximately 25-30% of patients with RCC are diagnosed with metastatic disease due to the lack of early symptoms and clinical indications of disease. ⁵ Prognosis is poor among metastatic renal cell carcinoma (mRCC) patients, with 5-year survival rates of 5-10%. ⁶ As the population ages and risk factors for RCC become more prevalent, the burden of mRCC is expected to grow. ¹⁻³

Among patients with relapse or stage IV and surgically unresectable RCC, the National Comprehensive Cancer Network (NCCN) recommends sunitinib and pazopanib as category 1, preferred first-line targeted therapy treatments. More recently, NCCN expanded its first-line RCC treatment recommendations to include cabozantinib after the Food and Drug Administration (FDA) approved cabozantinib for first-line treatment of mRCC in December 2017 based on the CABOSUN (NCT01835158) trial results. The CABOSUN trial was a randomized, open-label phase II multicenter study in 157 patients with intermediate and poor-risk previously untreated clear cell mRCC. Intermediate and poor risk were classified based on IMDC prognostic risk groups (favorable, intermediate and poor). Patients received cabozantanib (n=79) 60 mg orally daily or sunitinib (n=78) 50 mg orally daily (4 weeks on treatment followed by 2 weeks off) until disease progression or unacceptable toxicity.8 Estimated median progression-free survival (PFS) for patients taking cabozantanib was 8.2 months (95% confidence interval [CI]: 6.2, 8.8) compared with 5.6 months (95% CI: 3.4, 8.1) for patients taking sunitinib (hazard ratio for progression or death = 0.66; 95% CI: 0.46, 0.95; p=0.012). Based on these results, the NCCN guidelines recommended cabozantinib for first-line RCC treatment in poor- and intermediate-risk groups.

Findings from the CABOSUN trial showed that patients (IMDC intermediate and poor risk) taking sunitinib had a PFS of 5.6 months. This was lower than the results from a phase III trial that examined sunitinib versus interferon alfa in untreated clear cell mRCC patients where the PFS was 11.0 months in the sunitinib group vs. 5.0 months in the interferon alfa group. A recent retrospective analysis of the phase III trial demonstrated that, of the 373 patients treated with sunitinib, there were 36% favorable, 55% intermediate, and 9% poor based on the IMDC prognostic risk group. In addition, the median PFS for patients treated with sunitinib was 14.1 months (95% CI: 13.4, 17.1), 10.7 months (95% CI: 10.5, 12.5), and 2.4 months (95% CI: 1.1, 4.7) for favorable, intermediate, and poor risk groups, respectively. When intermediate and poor IMDC risk groups were combined. the median PFS was 10.6 months (95% CI: 8.1, 10.9). 10 CheckMate 214 was another phase III trial that compared nivolumab plus ipilimumab (nivo+ipi) with sunitinib for previously untreated clear cell mRCC. The results from this trial showed that among patients in the intermediate and poor IMDC risk groups, the median PFS was 11.6 months (95% CI: 8.7, 15.5) in the nivo+ipi vs. 8.4 months (95% CI: 7.0, 10.8) in the sunitinib. Of the 426 patients in the intermediate and poor risk groups, 334 (79%) and 91 (21%) patients were identified as intermediate and poor risk, respectively. 11 Based on the differences in PFS between these studies, patient IMDC prognostic risk group may play a role in the effect of first-line treatment on clinical outcomes.

In addition to differences between IMDC prognostic risk groups, heterogeneity may exist within a risk group as well. Specifically, patients with IMDC intermediate risk group (defined as having 1 or 2 IMDC risk factors) may have different clinical outcomes depending on the number of risk factors. A retrospective analysis of six clinical trials examining sunitinib treatment for mRCC reported that among patients in the intermediate risk group, time interval less than 1 year from RCC diagnosis to targeted therapy was the most common risk factor as observed in 36% of patients with 1 risk factor alone or in combination with low serum hemoglobin as observed in 25% of patients with 2 risk factors. The study also found that patients with 1 risk factor had longer OS (25.6 vs. 16.3 months) and PFS (9.8 vs. 8.6 months), and greater ORR (39.5% vs. 31.8%) when compared to those with 2 risk factors. 12 These results are comparable to those from the retrospective analysis of sunitinib vs. interferon alfa phase III trial, where the median OS in patients with 1 risk factor was 28.2 months vs. 16.3 months in those with 2 risk factors. ORR was 33.3% (95% CI: 25.9, 41.5) in patients with 1 risk factor and 31.7% (95% CI: 20.3, 45.0) in those with 2 risk factors. Median PFS in intermediate risk group patients with 1 or 2 risk factors was 10.7 months. 10

Given the high interest to examine the effect of lines of treatments on clinical outcomes by IMDC prognostic risk group, Analysis Group, Inc. (AGI) will conduct a study to further understand the clinical outcomes in mRCC patients treated with sunitinib as first-line stratified by IMDC prognostic risk groups in real-world clinical practices using the IMDC database. This will provide contemporary benchmarks for outcomes and survival among mRCC treated with first-line sunitinib in the real world. Additionally, the clinical heterogeneity within the IMDC intermediate risk group and impact of individual IMDC prognostic risk factors will be explored.

6. RESEARCH QUESTION AND OBJECTIVES

The study aims to address the following:

- 1. To describe patient demographic and clinical characteristics among all mRCC patients treated with sunitinib in first-line, stratified by IMDC prognostic risk score (ie, favorable, intermediate, and poor).
- 2. To characterize the following clinical outcomes in patients treated with sunitinib in first-line, stratified by IMDC prognostic risk groups and Karnofsky Performance Status (KPS).
 - OS;
 - Time to treatment discontinuation (TTD);
 - Reasons for treatment discontinuation:
 - Physician-assessed best response (objective response rate [ORR], progressive disease, stable disease).
- 3. To conduct a subgroup analysis assessing demographic and clinical characteristics and the following clinical outcomes among mRCC patients in the intermediate IMDC prognostic risk group, stratified by patients having only 1 IMDC risk factor versus 2 IMDC risk factors.
 - OS;
 - TTD;
 - Physician-assessed best response (ORR, progressive disease, stable disease).

[figure not shown]
7. RESEARCH METHODS

7.1. Study Design

This is a retrospective, longitudinal cohort study that involves the analysis of retrospective data collected through the IMDC database. A cohort of mRCC patients who initiated sunitinib as first-line therapy will be evaluated.

The index date will be defined as the date of initiation of first-line sunitinib therapy. The baseline period will be defined as the time from mRCC diagnosis to the index date. The follow-up period will be defined as the time from the index date to the earliest of death or end of data availability. Figure 1 depicts the study design scheme.

Figure 1. Study Design Scheme

7.2. Setting

7.2.1. Inclusion Criteria

1. Patients will be selected based on the eligibility criteria listed below. Participation in interventional trial for mRCC disease is allowed. Subjects will be selected irrespective of their survival status.

Patients must meet all of the following inclusion criteria to be eligible for inclusion in the study:

- Diagnosed with mRCC;
- Initiated treatment post mRCC diagnosis and received sunitinib as first-line therapy;
- Age 18 years or over at the time of mRCC diagnosis;
- Actively treated at an IMDC clinical center.

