7.3. Variables

Primary exposure

• Sunitinib as first-line therapy.

Outcomes

- OS, defined as the time between index date and death.
- TTD, defined as the time between index date and discontinuation of therapy due to any reason including progression, death, or toxicity.
- Reasons for treatment discontinuation, categorized as progression, death, toxicity, or other.
- Physician-assessed best response, defined as ORR (sum of partial response and complete response), progressive disease, and stable disease.

Covariates (assessed during the baseline period or at index date).

- Gender.
- Age at time of mRCC diagnosis.
- Race.
- Date of RCC diagnosis.
- Date of mRCC diagnosis.
- Prior nephrectomy.
- Date of nephrectomy (if applicable).
- Pathology.
 - Non clear cell RCC.
 - Clear cell RCC.
- Number of metastatic sites (eg., 1 site or more than 1 site).
- Site of metastases (eg, brain metastasis).
- IMDC prognostic risk factors.
 - Time from diagnosis to treatment initiation.
 - Karnofsky performance status at index date.
 - Serum hemoglobin at index date.

- Serum corrected calcium at index date.
- Neutrophil count (absolute count) at index date.
- Platelet count at index date.

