7.4. Data Sources

Data will be obtained retrospectively from the IMDC clinical sites.

The IMDC cohort is a multi-institutional cohort that collects data globally from 35 international cancer centers in the United States, Canada, Denmark, Greece, South Korea, Australia, New Zealand, Japan, Singapore, Italy, and Belgium. Demographic, clinical, laboratory, and outcome data on patients with mRCC are collected retrospectively from medical charts using uniform database templates and standardized definitions to ensure data are collected consistently. Medical records include longitudinal information on patient demographic and disease characteristics, oncology-specific workups and evaluations, treatment types and duration, concurrent diagnoses as documented in physician notes, and treatment discontinuation/halt decisions.

AGI will collaborate with [name] from the PPD who will serve as the principal investigator for this study and who is also the Chair of the IMDC, to obtain data from clinical centers. The clinical centers send data to the IMDC database, which is updated frequently (ie, quarterly or continuously). Data cleaning and consolidation of the data occur twice a year.

For this proposed study, a "limited" dataset of first-line sunitinib patients will be provided. The "limited" dataset will be anonymized and will not contain any personal data. All first-line sunitinib patients are included in the "limited" dataset, but only a select number of variables necessary to fulfill the study objectives will be included.

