7.7. Data Analysis

Identification of the Study Cohort

The study population of interest in the current study are patients treated with first-line sunitinib. Each patient's eligibility for study will be verified against the eligibility criteria.

Description of patient demographic and clinical characteristics among patients in the study cohort, stratified by IMDC prognostic risk group

Baseline demographic and clinical characteristics prior to the index date will be described using the mean (standard deviation [SD]) and median values for continuous variables and frequency distributions for categorical variables. Demographic and clinical characteristics will also be summarized, stratified by IMDC prognostic risk groups (ie, favorable, intermediate, and poor). Comparisons will be performed using chi-square tests or Fisher's exact test, as appropriate, for categorical variables and Wilcoxon-Mann-Whitney non-parametric tests for continuous variables.

Characterization of clinical outcomes of mRCC patients treated with first-line sunitinib

The following clinical outcomes will be stratified by IMDC prognostic risk groups (ie, favorable, intermediate, and poor) and KPS (eg, 0-40%, 50-70%, and 80-100%).

- OS and TTD will be analyzed using Kaplan-Meier estimator.
- Reasons for first-line sunitinib therapy discontinuation will be described using relative frequencies.
- Physician-assessed best tumor response (ie, objective response rate, stable disease, and progressive disease) to first-line sunitinib will be described using relative frequencies.

Indirect qualitative evaluation of the real-world clinical outcomes of mRCC patients treated with first-line sunitinib with that of phase II and III clinical trials

An indirect qualitative, side-by-side evaluation of clinical outcomes will be conducted between the following groups:

• Previously untreated sunitinib patients with intermediate or poor IMDC risk score from the real-world IMDC database *vs* previously untreated sunitinib patients with intermediate or poor IMDC risk score from the 1) CABOSUN trial, 2) CheckMate 214, and 3) sunitinib vs. IFN-α trial.

Subgroup analysis describing demographic and clinical characteristics and characterizing clinical outcomes among patients in the IMDC intermediate risk group, stratified by patients having only 1 vs 2 risk factors

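### Eligibility does not require first-line sunitinib to have been started under care at an IMDC center; if patients referred later are in the data, Kaplan-Meier OS from sunitinib start is overstated

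*Combined protocol and SAP*

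**What the plan says.** Section 7.2.1 (Inclusion Criteria) lists treatment and center as separate items. The treatment item reads "Initiated treatment post mRCC diagnosis and received sunitinib as first-line therapy" and gives no place of initiation. The center item reads "Actively treated at an IMDC clinical center" and names no drug, line of therapy or date. The same section adds that "Subjects will be selected irrespective of their survival status". Section 7.4 does not narrow the population: "All first-line sunitinib patients are included in the" limited dataset supplied for the study.

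On the time scale, Section 7.1 states "The index date will be defined as the date of initiation of first-line sunitinib therapy" and "The follow-up period will be defined as the time from the index date to the earliest of death or end of data availability". Section 7.3 gives "OS, defined as the time between index date and death", and Section 7.7 says "OS and TTD will be analyzed using Kaplan-Meier estimator". The plan defines no date of first contact with the center, no delayed entry, no landmark, and no analysis restricted to patients who started sunitinib at a center. Section 7.8 names selection bias only in general terms.

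**The concern.** Take a patient who starts sunitinib outside the consortium and comes to an IMDC center some months later, for example for second-line treatment. That patient meets every criterion in Sections 7.2.1 and 7.2.2. The clock starts at the first sunitinib dose, but the patient could be recorded only by being alive at referral. Comparable patients who died before referral are never recorded. Plain Kaplan-Meier counts the interval from index to referral as time at risk, although no recorded late referral could have died in it. This is left truncation, also called immortal time.

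Section 5 offers the results as current benchmarks for survival on first-line sunitinib. Section 7.7 sets the intermediate- and poor-risk results beside the sunitinib arms of three trials. A bias of this kind does not shrink as the cohort grows, and confidence intervals would not show it.

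**Working it through.** The plan gives no bias or sample-size figure to reproduce, so the check sizes the possible effect under stated assumptions.

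**Inputs from the documents (Section 5).** Median OS is 16.3 months with 2 risk factors, and 28.2 or 25.6 months with 1 risk factor (two sources). Median PFS is 9.8 months (1 factor) and 8.6 months (2 factors). These serve only as illustrative true values.

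**Assumed, not in the documents.** Exponential survival; the share f of the source population starting elsewhere; the time to referral.

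**Case A: referral independent of prognosis, exponential with mean 9 months.** Let λ = ln 2 / median and ρ = 1/9.

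- Probability that a late referral survives to be recorded: P = ρ/(λ+ρ).
- Share of late referrals among recorded patients: w = fP/(1 − f + fP).
- Survival from index among recorded late referrals: S_L(t) = [e^(−λt) − (λ/(λ+ρ))·e^(−(λ+ρ)t)]/P.
- Curve that plain Kaplan-Meier estimates: S(t) = (1 − w)e^(−λt) + w·S_L(t).

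For a median of 16.3 and f = 0.20: λ = 0.04252, P = 0.1111/0.1536 = 0.723, and w = 0.1446/0.9446 = 0.153. At t = 16.3, S_L = 0.660, so S = 0.847 × 0.500 + 0.153 × 0.660 = 0.5245 instead of 0.500. Solving S(t) = 0.5 gives 17.45 months.

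| True median | f | P | w | Median from plain Kaplan-Meier | 12-month OS, true → estimated |
|---|---|---|---|---|---|
| 16.3 | 0.10 | 0.723 | 0.074 | 16.86 | 60.0% → 61.3% |
| 16.3 | 0.20 | 0.723 | 0.153 | 17.45 | 60.0% → 62.6% |
| 28.2 | 0.10 | 0.819 | 0.083 | 28.91 | 74.5% → 75.5% |
| 28.2 | 0.20 | 0.819 | 0.170 | 29.65 | 74.5% → 76.5% |

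Simulation under the same shares and mean lag gives 16.8-17.4 and 29.0-29.7, which agrees to within about 0.1 month. Delayed-entry Kaplan-Meier returned 16.3 and 28.2.

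**Wider range.** A simulation of 400,000 patients per scenario used uniform referral times with mean 3, 6 or 12 months and f of 10%, 20% or 40%. Plain Kaplan-Meier gave 16.5-20.1 months against a true 16.3, and 26.0-29.8 against 25.6. Restriction to center-started patients, or delayed entry, returned the true value to within 0.2 months.

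**Case B: referral 0-3 months after progression.** Median time to progression or death was 9.8 or 8.6 months. It was assumed that 15% of first events are deaths and that median post-progression survival is 16 or 8 months.

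| True median OS (about) | f | Plain Kaplan-Meier | Delayed entry | Center-started only |
|---|---|---|---|---|
| 27.2 | 0.10 | 27.7 | 26.8 | 27.3 |
| 27.2 | 0.20 | 28.1 | 26.1 | 27.1 |
| 18.3 | 0.10 | 18.6 | 17.9 | 18.3 |
| 18.3 | 0.20 | 18.8 | 17.4 | 18.3 |

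Plain Kaplan-Meier overstates by 0.3-0.9 months. Delayed entry now understates by 0.4-1.1 months, because the referral time carries information about prognosis. Restriction recovers the true median.

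**Scale.** With exponential survival, no censoring, a median of 16.3 and 2,500 patients (Section 7.5 gives 2,000-3,000), the standard error of the Kaplan-Meier median is 1/(λ√n) = 1/(0.04252 × 50) ≈ 0.5 months. Standard errors within strata are larger.

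**The case against.** The strongest reply is that nothing in the documents shows that any patient started sunitinib elsewhere. The center item stands in a list that defines a first-line sunitinib cohort, so it can fairly be read as active treatment for that line. In addition, Section 7.3 takes KPS, hemoglobin, corrected calcium, neutrophils and platelets at the index date, and Section 7.7 stratifies outcomes by risk group and KPS. A referred patient reaches the stratified curves only if outside records supply those values. The study is descriptive, and the comparison with trials is qualitative, with no test or decision rule.

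Much of this stands. It makes the size of the effect uncertain and any assumed share less secure in the stratified curves. It does not close the gap. The favorable reading is not written down, and the index-date values are covariates, not an eligibility rule. Selecting patients whether or not they are still alive admits recorded patients who later died; it does not recover those who died before reaching a center. The general mention of selection bias in Section 7.8 gives no direction and plans no analysis.

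A reader might infer three stronger things that the documents do not support:

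- **That the OS results are biased upward.** That needs late referrals to exist, and their number is not given.
- **That short TTD and deaths on drug are under-counted.** The direction for TTD is uncertain. Deaths on drug before referral are missed, but referral after early discontinuation could pull TTD the other way.
- **That delayed entry is an equivalent cure.** Case B shows that it over-corrects when progression triggers referral.

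**Conclusion.** The gap in the eligibility text is real and can be verified from the wording. The bias is conditional: OS is overstated only if late-referred patients are in the data. With 10-20% of the source population referred late, the overstatement of median OS is about 0.5-1.5 months when referral is independent of prognosis at a mean of 9 months, and about 0.3-0.9 months when it follows progression. It is zero with no such patients, and a worse case mix among referred patients could offset it. All magnitudes rest on assumed shares, referral times and exponential survival. This is an inexpensive improvement to the plan, not a demonstrated error in its results.

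**What to change.** Reword the center criterion in Section 7.2.1 to *initiated first-line sunitinib while under care at an IMDC clinical center*, and make that the primary OS population.

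If referred patients are to be kept:

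1. Request the date of first contact with the center.
2. Report how many patients started sunitinib elsewhere.
3. Show OS restricted to center-initiated patients as the primary result.
4. Use delayed-entry Kaplan-Meier, with entry at first center contact, only as a sensitivity analysis, and state that it can over-correct when progression triggers referral.

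The cost is one sentence and the loss of some patients, or one additional date field in the limited dataset.

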7.2.2. Exclusion Criteria

- Initiated first-line sunitinib treatment before 2010;
- Had non-clear cell mRCC.

7.3. Variables

Primary exposure

• Sunitinib as first-line therapy.

Outcomes

- OS, defined as the time between index date and death.
- TTD, defined as the time between index date and discontinuation of therapy due to any reason including progression, death, or toxicity.
- Reasons for treatment discontinuation, categorized as progression, death, toxicity, or other.
- Physician-assessed best response, defined as ORR (sum of partial response and complete response), progressive disease, and stable disease.

Covariates (assessed during the baseline period or at index date).

- Gender.
- Age at time of mRCC diagnosis.
- Race.
- Date of RCC diagnosis.
- Date of mRCC diagnosis.
- Prior nephrectomy.
- Date of nephrectomy (if applicable).
- Pathology.
 - Non clear cell RCC.
 - Clear cell RCC.
- Number of metastatic sites (eg., 1 site or more than 1 site).
- Site of metastases (eg, brain metastasis).
- IMDC prognostic risk factors.
 - Time from diagnosis to treatment initiation.
 - Karnofsky performance status at index date.
 - Serum hemoglobin at index date.

- Serum corrected calcium at index date.
- Neutrophil count (absolute count) at index date.
- Platelet count at index date.

